### **6.4 Blinding**

This is an open-label study; therefore, the subjects and investigators will be unblinded to subject's sequence. However, there will be a limited degree of blinding in the data review and data analysis process. In particular, PMI and CRO personnel will be blinded to the randomized sequence as summarized in the following table:

Data and information contained in this document are considered to constitute trade secrets and confidential commercial information, and the legal protections provided to such trade secrets and confidential information are hereby claimed under the provisions of applicable law. No part of this document may be publicly disclosed without the written consent of Philip Morris Products S.A.

Blinded Study Personnel	End of Blinding Period
PMI and CRO study statisticians	After the Statistical Analysis Plan (SAP) finalization or PMI blind database review (*) , whichever comes last.
PMI data manager	After the finalization of PMI blind database review. (*)
PMI safety and clinical scientist	After the finalization of PMI blind database review (*) . Can be actively un-blinded before that time point in case of the occurrence of any safety question, when appropriate.

(\*) As part of the PMI Quality Control (QC) activity, data listings will be reviewed by PMI before database lock, with no access to the randomization sequence information.

Any PMI and CRO personnel who are not listed in the above table will be unblinded by default.

## 6.5 Investigational and Reference Point Product Accountability and Compliance

### 6.5.1 Dispensing Investigational and Reference Point Products

From Day -1 until Day 4, the THS 2.2, NNS, and CC will be dispensed by the Investigators or dedicated study staff, as per study design. Each dispense of the product will be recorded in a log. The log should include subject number, date and start time of product use. The product will not be promoted for commercial distribution or test market.

### 6.5.2 Storage and Accountability

The THS 2.2, NNS, and CC will be stored in a secured site storage place with access limited to the authorized personnel only. Full accountability of the distributed products will be ensured by designated staff. Subjects will return each butt of any used Tobacco Stick or CC immediately after use to the site staff for accountability. They will also return the NNS after use to the site staff. This will be documented in appropriate log. At the end of the study, unused CCs given to the site staff at Admission on Day -1 will be given back to the subjects.

Data and information contained in this document are considered to constitute trade secrets and confidential commercial information, and the legal protections provided to such trade secrets and confidential information are hereby claimed under the provisions of applicable law. No part of this document may be publicly disclosed without the written consent of Philip Morris Products S.A.

### 6.5.3 **Investigational and Reference Point Product Retention**

Unused Tobacco Sticks and NNS will be destroyed if possible, or returned to the Sponsor upon study completion. The Tobacco Heating Devices will be returned to the Sponsor.

### 6.5.4 **Compliance to Investigational and Reference Point Products**

Compliance for all arms will be ensured by strict distribution of the products (product by product) and collection of used Tobacco Sticks, the CC butts and the NNS after use will be documented in appropriate logs.

In addition, in subjects using NNS, the compliance will be chemically verified using exhaled CO breath. The cut-off point for the CO breath test value to distinguish tobacco use vs. no tobacco use will be 10 ppm ([Benowitz et al, 2002](#)).

Furthermore, the CO breath test will be considered as one of the measures of compliance during the wash-out days in all subjects.

## 6.6 **Restrictions**

### 6.6.1 **Smoking Restrictions**

On Day 1 and Day 3, to avoid nicotine cross contamination, smokers of THS 2.2 and CC will smoke in dedicated separate rooms: one room for THS 2.2 and one room for CC. Every subject must smoke alone with an interval between subjects allowing ventilation of the room. Subjects receiving NNS must not have access to these rooms.

In the morning prior admission, subjects will be instructed not to smoke. At admission, smoking is only allowed during the designated smoking times from 6:00 am to 11:00 PM as detailed in the study design. Subjects will not have free access to their NNS, CC or Tobacco Sticks, which will be dispensed by the site staff individually as described in [Section 6.5.1](#).

Smoking is not allowed during study procedures except during blood sampling for nicotine PK on Day 1 and Day 3. Furthermore, smoking is not allowed on Day 4 until all laboratory tests and the spirometry have been conducted.

During the days of wash-out or single product use (for CC and THS 2.2 arms), no NNS or other products supportive to smoking abstinence must be used or will be provided to the subjects.

## 6.6.2 Dietary Restrictions

A standard diet will be designed by a dietician for the whole confinement period. For each meal, the caloric and fat content should be controlled in order to avoid a “high-fat” diet. The FDA guidance on food-effect studies for bioequivalency testing identifies a “high-fat” diet as a diet which contains “approximately 50 percent of total caloric content of the meal [from fat] and is high in calories (approximately 800 to 1000 calories) ([FDA, 2002](#)).

Subjects are not allowed to bring their own food or beverages to the investigational site. Meals will be served according to the schedules provided in [Sections 9.2, 9.3.1, 9.3.2](#) and [9.4](#). Additional light snacks, fruits, and raw vegetables can be distributed to the subjects without restrictions at any time during confinement as long as they comply with the dietician’s standard diet. Consumption of water is allowed as desired. Consumption of quinine-containing drinks (e.g., tonic water) is not allowed. The same menu and meal schedule will be administered uniformly for all subjects in all study arms. Fasting state has to be observed for at least 10 hours prior to blood drawings for the safety laboratory on the Screening Visit, on Day -1 and Day 4.

## 6.7 Concomitant Medication

For the purpose of this study, no concomitant medication should be taken by the subjects. Any medication with an impact on the CYP2A6 metabolism (as prescription and over-the-counter products) as given below must be avoided as CYP2A6 is involved in the nicotine metabolism.

In this study the use of hormonal contraception containing oestrogens is NOT allowed. This also applies to hormone replacement therapy. Only hormonal contraception with products containing progesterone is allowed during this study. Subjects using oestrogens during the study will be withdrawn.

The following drugs and substances are considered as having an impact on CYP2A6 activity ([Lacy et al, 2007: Table 2](#)). Prior to database close, the concomitant medication will be assessed according to the potential impact on CYP2A6 activity and the potential impact on study results.

**Table 2. Examples of Drugs and Substances Considered Interacting with CYP2A6**

Drug name	Substance Class
Fluoroquinolones, including ciprofloxacin and ofloxacin, nafcillin, rifampicin	Antibiotic
Fluvoxamine, fluoxetine, paroxetine, bupropion, duloxetine, amitriptyline, imipramine, sertraline, mirtazapine, citalopram, thioridazine	Antidepressant
Haloperidol, perphenazine, chlorpromazine, propoxyphene fluphenazine, clozapine, olanzapine	Neuroleptic
Phenobarbital, primidone, carbamazepine	Antiepileptic
Chlorquine, quinidine	Antirheumatic
Clotrimazole, terbinafine, fluconazole, ketoconazole, miconazole	Antimycotic
Erythromycin, ciprofloxacin, clarithromycin, norfloxacin	Antibiotic
Cimetidine, chlorpheniramine, diphenhydramine, ranitidine	H2-receptor antagonist
Amiodarone, verapamil, mibepradil, mexiletine, propafenone, propranolol, lidocaine	Antiarrhythmic
Losartan, amlodipine, nifedipine, losartan	Antihypertensive
Drospirenone, oestrogens	Hormonal contraceptives Agents for hormonal replacement therapy (oestrogens)
Fluvastatin	Cholesterol-lowering agent
Theophylline	Antispasmodic pulmonological agent/Bronchodilator agent
Omeprazole, Lansoprazole	Proton pump inhibitor
Interferon	Antiviral/Immunomodulating agent
Methoxsalen	Anti-psoriatic (substance class Furocoumarins)
Modafinil, Diclofenac, Rofecoxib	Analgesic
Insulin	Anti-diabetic

Data and information contained in this document are considered to constitute trade secrets and confidential commercial information, and the legal protections provided to such trade secrets and confidential information are hereby claimed under the provisions of applicable law. No part of this document may be publicly disclosed without the written consent of Philip Morris Products S.A.

Sildenafil	Phosphodiesterase-Inhibitor (e.g., used for treatment of Erectile dysfunction)
Quinine	Crystalline alkaloid
St. John's Wort	Over-the-counter (herbal remedy) antidepressant
Psoralen	Anti-psoriatic (substance class Furocoumarins)
Pilocarpine	Cholinergic agonists (e.g., used for Glaucoma Therapy)

Data sources: [Lacy et al, 2007](#). This list is not exhaustive.

However, the Investigator is responsible for the medical care of the subjects during their participation in this study. Any decisions regarding the prescription of medication will be taken in the best interest of the subject.

If the use of a concomitant medication cannot be avoided for the subject's safety it has to be fully documented (for details, see [Section 7.4.6](#)). Concomitant medications should be followed up with the CRO Medical Monitor on an ongoing basis.

Concomitant medication will first be assessed at Screening Visit. To be eligible for the study any medication with impact on CYP2A6 metabolism must be discontinued at least 14 days prior to Admission to the clinic or for at least five half-lives (whichever is longer). They must not be used during the entire study until the time of discharge. It is at the discretion of the Investigator to assess if a termination of such medication at Screening is medically justified and safe for the subject.

## 7 STUDY PROCEDURES

Personnel performing study measurements or recording must have the appropriate training fully documented. Quality and control measures have to be in place. All study procedures are provided as an overview in the Schedule of Events ([Appendix 1](#)). In this Section, only the expected/planned time points for the various measurements are given. Considering that not all subjects can have a procedure at the same time point, adequate time windows will be given for each study procedure and each time point in [Section 9](#). Site personnel will adhere to the site's Standard Operating Procedures (SOPs) for all activities. Appropriate medical advice will be provided to the subject in case of any medical findings requiring health care.

### 7.1 Informed Consent

Each subject must give his/her informed consent prior to participating in the study. During the consent process, the Investigator or designee obtaining consent must inform each subject of the nature, risks and benefits of, and alternatives to study participation. In addition, each subject must review the Subject Information Sheet and ICF and must have sufficient time to read and understand and have adequate opportunity to ask questions. The ICF must be signed and dated prior to undertaking any study-specific procedures. A signed copy should be given to the subject.

### 7.2 Smoking Cessation Advice and Debriefing

Each subject will be given advice on the risks of smoking three times during the study: at the Screening Visit, at Admission (Day -1), and at Day of Discharge (Day 4). This will take the form of a brief interview according to current World Health Organization (WHO) recommendations ([Raw et al, 2002](#)). Details of the interview will be recorded in the Source Document File. Information on the risks of smoking will be given to the subjects on an individual basis during a face-to-face meeting between the subject and the Investigator or designee and may additionally be given in a group session.

In addition to the smoking cessation advice, a debriefing of subjects will be done at each smoking cessation advice session to address any intended or unintended beliefs participants have about the candidate MRTP. The goal of the debriefing would be to help ensure that subjects exit the study with an accurate understanding of product risks, including an understanding that the candidate MRTP has not been demonstrated to be less harmful.

## 7.3 Support during Smoking Abstinence/Periods of Reduced Smoking

All subjects will be closely monitored by the site staff on D0, D1, D2, and D3. This includes monitoring of clinical tests e.g., vital signs, physical examination, and body weight. It also refers to close monitoring of the subject's behaviour, AEs, and his/her mood.

## 7.4 Clinical Assessments

Any clinically relevant finding detected during the Screening Visit has to be documented as a concomitant disease. This also applies to clinically relevant findings in e.g., laboratory values, vital signs and ECGs, detected during the Screening Visit. Any untoward medical occurrence in a subject detected during the study which was not present at the Screening Visit must be documented as an AE. Worsening of a pre-existing condition from the Screening Visit onwards will also be documented as an AE. If a clinically relevant finding is detected during the Screening period, the Investigator needs to check if inclusion criterion no. 3 is still fulfilled.

### 7.4.1 Demographic Data

Demographic data (sex, date of birth/age, and race) will be recorded on the day of ICF signature.

### 7.4.2 Socio-Economic Status

At Day 2, subjects will be asked questions, which will allow the Sponsor to infer their socio-economic status (see [section 7.8.5](#)).

### 7.4.3 Identification of the Current Cigarette Brand

Identification of the current CC brand smoked by the subject will be done at the Screening Visit and at Day -1. For the Screening Visit, smokers will be asked to bring a packet of their current CC brand to the site. The site staff will document brand name and yields. At Day -1, subjects have to hand their CC supply for the confinement period to the site staff, who will take a photograph of the front and of the side of a cigarette pack with information of ISO nicotine , CO and tar supplied by the subject and will document brand name and yields. Photos will be considered as Source Documentation. A copy of the photos will be provided to the Sponsor electronically as Digital Versatile Disc (DVD) or Compact Disc (CD).

#### 7.4.4 Smoking History and Willingness to Quit Smoking

Subjects will be questioned for their smoking history. At Screening and day of Admission, this will include questions to evaluate whether the subject was a smoker for at least the last three consecutive years, to determine the number of CC smoked during the previous 4 weeks, and to evaluate if the CCs smoked during the previous 4 weeks were non-menthol. Yields will later be ascertained, from the cigarette brands. At the Screening Visit only, the subject will also be asked if he/she is planning to quit smoking during the next 3 months. In addition, the subject will be asked if he/she has used nicotine-containing products other than commercially available CC (either tobacco-based products or NRT), electronic cigarettes or similar devices, within 4 weeks prior to assessment.

Furthermore, subjects will be asked if they are ready to abstain from smoking/accept reduced smoking frequency for up to 4 days. Only subjects prepared and able to comply with this requirement will be considered for participation in the study.

#### 7.4.5 Demonstration and Product Tests of THS 2.2 and NNS

All subjects will have a demonstration of the THS 2.2 and the NNS products by the site staff at the Screening Visit. On Day -1, as the last procedure of the eligibility assessments, subjects will have a product test for the THS 2.2 (using up to three Tobacco Sticks) first and subsequently a product test of the NNS (spraying once in each nostril). In female subjects, the THS 2.2 and NNS product tests must only be done after pregnancy is excluded by a negative urine pregnancy test. Only subjects willing and ready to use the THS 2.2 and the NNS and be randomized to any of the study arms can be enrolled into the study.

#### 7.4.6 Medical History, Concomitant Disease, Previous and Ongoing Medications

Relevant medical history and any concomitant disease will be documented at the Screening Visit. Medical history is defined as any condition that started prior to and ended prior to Screening. A concomitant disease is defined as any condition that started prior to the Screening Visit and is still ongoing at the Screening Visit.

Medication taken within 4 weeks prior to Screening Visit and any concomitant medication needs to be documented. Any medication which was started prior to the Screening Visit and is still being taken by the subject will be considered a concomitant medication. Medication initiated after Screening is also referred to as concomitant medication. This applies to both prescription and over-the-counter products.

Records should include the drug name (preferably both generic and trade name), route of administration, (e.g., oral, intravenous), total daily dose/unit (expressed in, for example, mg, mL, or IU), indication, the start and, if applicable, the stop date (day, month, and year). Therapy changes (including changes of regimen) during the study are to be documented. If a concomitant medication is still being taken by the subject at the end of the study, this will be recorded on the eCRF.

#### 7.4.7 Physical Examination

A physical examination will be conducted at the Screening Visit, at Admission (Day -1) and at the Day of Discharge (Day 4).

#### 7.4.8 Body Height and Weight

Body weight will be recorded at the Screening Visit, at Admission (Day -1) and at the Day of Discharge (Day 4). Body height will be measured at the Screening Visit, only. The BMI will be calculated from the body weight and height using the following formula, rounded to one decimal place:

$$\text{BMI} = \frac{\text{weight in kilograms}}{\text{height in meters}^2} = \frac{\text{kg}}{\text{m}^2}$$

#### 7.4.9 Vital Signs

Systolic and diastolic blood pressure, pulse rate, and respiratory rate will be measured at the Screening Visit, at Admission, and at every day in confinement. All parameters will be recorded in supine position after the subject has rested for at least 5 minutes.

For every measurement it has to be documented if the subject has smoked within 15 minutes prior to the measurement.

#### 7.4.10 Other Clinical Assessments

##### 7.4.10.1 Spirometry

Spirometry with and without a short-acting bronchodilator will be done at the Screening Visit to evaluate inclusion/exclusion criteria (the post-bronchodilator results). At screening, spirometry without bronchodilator will be done first, and then, spirometry with bronchodilator. Furthermore, spirometry without a bronchodilator will be performed on Day-1 as well as on Day 4.

Data and information contained in this document are considered to constitute trade secrets and confidential commercial information, and the legal protections provided to such trade secrets and confidential information are hereby claimed under the provisions of applicable law. No part of this document may be publicly disclosed without the written consent of Philip Morris Products S.A.

Spirometry will follow the 2005 testing and quality recommendations by the American Thoracic Society/European Respiratory Society Joint Task Force on the standardization of spirometry along with the electronic data submission and documentation processes ([American Thoracic Society \(ATS\), 2005](#)). Spirometry predicted values will be standardized to the National Health and Nutrition Examination Survey III predicted set ([Hu and Cassano \(NHANES III\), 2000](#)).

All personnel performing lung function testing should have the appropriate training and quality control measures should be put into place and be properly documented and filed at the pulmonary function laboratory (including the records of the calibration, if applicable). The FEV1 and FVC will be recorded.

The subject will be submitted to a spirometry with maximum voluntary ventilation measurement.

For spirometry, assessed parameters will include:

- FEV1.
- FVC.
- FEV1/FVC.

#### 7.4.10.2 Electrocardiogram

An ECG will be recorded at Screening and on the following study days: Day 1 and Day 3. The ECG testing will be performed as per the site local practice. A standard 12-lead ECG will be recorded after the subject has rested for at least 10 minutes in supine position.

The following parameters will be documented: heart rate, PR interval, QRS interval, QT interval and QTc interval, corrected by the ECG device according to Bazett's formula. Every ECG has to be assessed as normal, abnormal – clinically not relevant, or abnormal – clinically relevant. A diagnosis has to be provided in the eCRF for all ECGs assessed as abnormal – clinically relevant. ECG print-outs will be interpreted by a qualified physician. Any print-outs of ECGs on thermo-sensitive paper must be photocopied, initialled, dated, and stapled together for inclusion in the Source Data File.

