## 6.2 Use of Investigational and Reference Point Products

Subjects will never be requested or forced to smoke and will be free to stop smoking at any time during the study. Subjects caught using any nicotine/tobacco product which is different from the assigned product will be withdrawn from the study. During the screening period, subjects will be allowed to smoke according to their smoking habits except during the procedures of the screening visit 9.1 at the discretion of the site.

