**Table 8. Time Schedule – Day 1 and Day 3 Single Use**

Time	Blood sample	Procedures	Additional information
Start of procedure			
		Optional: light snacks prior first blood draw of the day	
		AE/SAE recording, concomitant medication	All day
		Support as required	All day
		Craving questionnaire (QSU-brief)	First time prior to T0, then 15 min +5 min, 30 min +5 min, 45 min +5 min, 1 hr +5 min, 2 hrs +5 min, after T0, then and 4 hrs +10 min, 6 hrs +10 min, 9 hrs +10 min, and 12 hrs +10 min
√		Plasma nicotine sample	First sample within 15 min prior to T0, 15 samples thereafter in relation to T0: T1 after 2 min +1 min, T2 after 4 min +1 min, T3 after 6 min +1 min, T4 after 8 min +1 min, T5 after 10 min +1 min, T6 after 15 min +2 min, T7 after 30 min +2 min, T8 after 45 min +2 min, T9 after 60 min +3 min, T10 after 2 hrs +5 min, T11 after 4 hrs +5 min, T12 after 6 hrs +5 min, T13 after 9 hrs +5 min, T14 after 12 hrs +5 min, and T15 after 24 hrs +5 min)
√		COHb blood sampling	Five blood samples to be taken, first sample within 15 min prior to T0, then after 15 min +2 min, 60 min +3 min, 4 hrs +5 min, 12 hrs +5 min
		CO breath test	First test to be done within 15 min prior to T0
		Assessment of cough	Has to be done prior to product use

Data and information contained in this document are considered to constitute trade secrets and confidential commercial information, and the legal protections provided to such trade secrets and confidential information are hereby claimed under the provisions of applicable law. No part of this document may be publicly disclosed without the written consent of Philip Morris Products S.A.

6:00 AM-9:00 AM	Start of single product use	
7:30 AM-10:00 AM	Breakfast	
10:00 AM-11:30 AM	Vital signs	At least 5 min in supine position prior to measurement
10:00 AM-11:30 AM	ECG	At least 10 min in supine position prior to recording
12:00 PM-1:30 PM	CO breath test	
1:00 PM-2:30 PM	Lunch	
4:00 PM-5:30 PM	CO breath test	
5:00 PM-5:30 PM	Snacks	
6:30 PM-9:00 PM	Dinner	
8:00 PM-9:30 PM	CO breath test	
8:00 PM-11:00 PM	Product evaluation questionnaire (MCEQ; only in sequence 1 and 2)	
	Collection of used Tobacco Sticks and CC butts and NNS	After the product use

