#### 12.6.5 Safety Endpoints

In general, all safety data will be listed and tabulated on the safety population by sequence, using the approach described in [Section 12.1.3](#). Safety variables collected during exposure periods will also be reported by product exposure.

AE data will serve as the primary assessment of safety. Other safety variables monitored in this study include: respiratory symptoms (cough assessment VAS and Likert scales); vital signs (systolic and diastolic blood pressure, pulse rate, respiratory rate); spirometry; ECG data; clinical chemistry, haematology, and urine analysis safety panel; physical examination; and concomitant medication.

The number and percentage of subjects with AEs and SAEs will be tabulated by system organ class and preferred term. Summaries will also be presented for AEs leading to withdrawal, AEs leading to Death, AEs by relatedness to product exposure, AEs by severity, and laboratory AEs. Tabulations will be performed for both the number of subjects experiencing an event and the number of events. The number and percentage of device events and of subjects with device events will be tabulated by sequence.

Data and information contained in this document are considered to constitute trade secrets and confidential commercial information, and the legal protections provided to such trade secrets and confidential information are hereby claimed under the provisions of applicable law. No part of this document may be publicly disclosed without the written consent of Philip Morris Products S.A.

The number and percentage of subjects with clinical findings will be tabulated by sequence for laboratory parameters. Shift tables showing change from baseline of clinical findings will be provided for ECGs, physical examinations, and laboratory parameters (both shifts in normal ranges and toxicity grades). Descriptive statistics will be summarized by visit and change from baseline for laboratory parameters, ECG, respiratory symptoms, and vital signs.

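### QTc is specified with Bazett's correction only, so its change from the Screening ECG can carry heart-rate artefact if heart rate differs between Screening and the use days

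*Protocol*

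**What the plan says.** Section 7.4.10.2 sets the ECG schedule and variables. On timing: "An ECG will be recorded at Screening and on the following study days: Day 1 and Day 3". On content, heart rate, PR and QRS are documented together with "QT interval and QTc interval, corrected by the ECG device according to" Bazett's formula. No second correction is named. On conditions: "A standard 12-lead ECG will be recorded after the subject has rested for at least 10 minutes in supine position".

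Section 12.1.2 defines baseline as the last available time point before T0 on Day 1. Table 8 puts the use-day ECG at "10:00 AM-11:30 AM", and Section 6.2.2 puts T0 between 6:00 and 9:00 AM, so the Day 1 ECG is always after product use. There is no ECG at Admission or on Day 0. The Screening ECG is therefore the effective baseline.

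Section 12.6.5 plans: "Descriptive statistics will be summarized by visit and change from baseline for laboratory parameters, ECG, respiratory symptoms, and vital signs". It also reports safety variables from the exposure periods by product exposure.

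On smoking state, Section 6.2 says: "During the screening period, subjects will be allowed to smoke according to their smoking habits", with an exception for the procedures of the Screening Visit. Section 6.2.2 requires nicotine abstinence from 11:00 PM on Day -1 until the single use on Day 1, and again from that use until the single use on Day 3. The nasal-spray label text in Appendix 4 includes decreased heart rate among possible withdrawal symptoms, without a figure.

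**The concern.** Bazett's formula divides QT by the square root of RR. If the true dependence of QT on RR is weaker than a square root, part of the heart-rate effect stays in QTc: the corrected value drifts down when the pulse slows and up when it quickens, with repolarisation unchanged. That matters little when baseline and follow-up ECGs are taken in the same state. Here they are not. The baseline belongs to a habitual smoker; the follow-up belongs to someone who has abstained for more than a day and then used one product.

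If heart rate falls between the two, Bazett QTc falls too and could mask a true lengthening in the change-from-baseline table. If heart rate rises, the table could show a lengthening that is only a faster pulse. With Bazett alone, a reader of the QTc summary cannot separate the two.

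**Working it through.** The protocol gives no QTc or heart-rate figure, so there is no stated number to reproduce. The check has two parts: the timing, which comes from the protocol, and the size of the artefact, which rests on assumed values.

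**Timing (Sections 6.2.2, 4.2 and Table 8)**
- Abstinence before Day 1 use: 11:00 PM on Day -1 to between 6:00 and 9:00 AM on Day 1 = 31 to 34 h.
- ECG after use: shortest 9:00 to 10:00 AM = 1 h; longest 6:00 to 11:30 AM = 5.5 h.
- Nicotine remaining, with the half-life of about 2 h in Section 4.2: 0.5^(1/2) = 71% at 1 h; 0.5^(5.5/2) = 15% at 5.5 h. This is simple exponential decay, used only as a guide. Abstinence and residual nicotine may pull heart rate in different directions, so the documents do not fix the sign of the net change from Screening.

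**Size of the artefact (assumed values)**

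Let RR = 60/HR in seconds and suppose QT = 400 × RR^b ms, with no true change in repolarisation. Then

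- Bazett: QTcB = QT/RR^0.5 = 400 × RR^(b − 0.5)
- Fridericia: QTcF = QT/RR^(1/3) = 400 × RR^(b − 1/3)

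With b = 1/3, QTcB = 400 × RR^(−1/6):
- 60 to 70 bpm: 400.0 to 410.4, a change of +10.4 ms.
- 80 to 70 bpm: 419.6 to 410.4, a change of −9.2 ms.
- From 75 bpm: falls of 5, 10 and 15 bpm give −4.7, −9.8 and −15.2 ms; rises of 5 and 10 bpm give +4.5 and +8.8 ms.

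Bazett artefact for a 10 bpm fall, by exponent and starting rate:

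| b | from 65 | from 70 | from 75 | from 80 |
|---|---|---|---|---|
| 0.25 | −16.7 | −15.7 | −14.9 | −14.1 |
| 1/3 | −11.1 | −10.4 | −9.8 | −9.2 |
| 0.40 | −6.7 | −6.2 | −5.8 | −5.5 |
| 0.50 | 0.0 | 0.0 | 0.0 | 0.0 |

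The range over b = 0.25 to 0.40 is about −5.5 to −16.7 ms. The artefact is zero if heart rate does not change or if b = 0.5.

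**Does the remedy depend on b being exactly 1/3?** For a fall from 75 to 65 bpm:
- b = 0.25: QTcF goes from 407.5 to 402.7 (−4.8 ms), against −14.9 ms for Bazett.
- b = 0.40: QTcF goes from 394.1 to 397.9 (+3.8 ms), against −5.8 ms for Bazett.

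The cube-root correction leaves a smaller residue in both cases, though not zero.

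**Can it be derived from what is recorded?** Yes. At 75 bpm with QT 371.3 ms, RR = 0.8 s, so QTcB = 371.3/0.8^0.5 = 415.1 ms and QTcF = 371.3/0.8^(1/3) = 400.0 ms.

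**The case against.** The strongest reply is that Section 7.4.10.2 only lists what the device documents. Section 12.6.5 names no QTc formula, and Section 12.1 leaves full analysis details to the statistical analysis plan, which was not available here and may add a second correction. Raw QT and heart rate are kept, so nothing is lost. This stands as a limit on severity. Even so, the protocol does name a method, and Bazett is the only one it names.

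A reader might infer more than the documents support, in three ways:

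- **That heart rate is expected to differ, so QTc changes will be biased in a known direction.** The protocol states no expected difference. Appendix 4 lists decreased heart rate only as a possibility, and the ECG falls at a time when residual nicotine varies widely. The direction of any artefact follows from the heart-rate change, whose sign is open. Supine rest of at least 10 minutes and the bar on smoking during procedures (Sections 6.2 and 6.6.1) also limit acute differences at Screening.
- **That product comparisons are equally affected.** The Day 1 and Day 3 ECGs share the clock window, the rest rule and prior abstinence, so the Screening state largely cancels. Only a product-specific heart-rate effect would remain, and the protocol gives no figure for one.
- **That a safety conclusion is invalidated.** ECG is a descriptive variable; adverse events are the primary safety assessment. There is no QT objective, test or threshold, and a physician reads every ECG. ECG heart rate is documented, and pulse is taken in the same window and summarised, so a rate shift would be visible elsewhere in the report.

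It is also fair to say that the 9 to 10 ms figure assumes the cube-root relation, under which the cube-root correction wins by construction. That is why a range of exponents is shown.

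**Conclusion.** The point holds as a minor improvement. The protocol fixes Bazett as the only QT correction and plans a change from a baseline ECG taken in a different smoking state from the use-day ECGs. Change in Bazett QTc from Screening can therefore carry heart-rate artefact.

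Its size is conditional. It is about 9 to 10 ms per 10 bpm under a cube-root relation near 60 to 80 bpm, and about 5.5 to 17 ms for a 10 bpm fall over exponents of 0.25 to 0.40. It is nil if heart rate does not move. The heart-rate shift, the exponents and the starting rates are all assumptions; the documents supply only the difference in state and an unquantified mention of slower heart rate on withdrawal. The concern is mainly with change from Screening. No pharmacokinetic result depends on it.

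**What to change.** In Section 7.4.10.2 or 12.6.5, add a derived variable QTcF = QT/RR^(1/3), with RR = 60/heart rate in seconds, computed from the QT and heart rate on the same ECG. Summarise it by visit, change from baseline and product exposure, beside the device's Bazett QTc and the ECG heart rate. With the three side by side, a reader can judge whether a QTc change goes beyond what a change in pulse would produce.

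The cost is one derived variable and one table. No extra ECG or new data item is needed.
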